### **Preliminary results Fitforlife pilot study**

During 2015-2016, 99 participants were included. A majority were males (60 persons) and the mean age was 28.2 years. The study was originally designed as a waiting list study but due to

problems with the open care units this turned out to be impossible. Of the 99 persons 39 did not attend any sessions, the rest attended between 1-52 sessions, mean 13.1(SD 12.1). Trailmaking A test time (visual attention) improved 8.5 seconds (SD 20.4) in those that attended >1 session and 5.4 (SD 6.5) in those that did not attend. Trailmaking B, (visual attention and task shifting), improved 10.4 seconds (SD 42.8) in attenders versus 4.6 (SD 31.7) in non-attenders.

Camberwell assessment of need showed that at the initial examination 33 persons reported difficulties with social contacts while at the end of the intervention 17 of those reported no problems. Likewise, 24 persons reported problems with close relations at baseline while 11 of them reported no problem at the end. In the proposed study this will be measured in a more extensive way. During an open house for participants and relatives there were reports about improvement in daily life such as "started to care about his looks", "cleans his room". During spring 2017 the cognitive tests will be analysed and linked with inflammatory markers. The study has given us experience on how to organise exercise for persons with psychosis. After the first wave four participants were educated as peer mentors. At least one peer-mentor was present in all sessions in wave two and three. The peer mentors were responsible for organizing parts of the sessions under supervision of educated trainers. Since the study finished the mentors have worked as peer mentor trainers, offering sessions to patients at an open care unit for FEP. The staff promote the sessions during their meetings with their patients and discussion about physical activity levels is a part of all patients' individual care programme.

**Study objectives:** See separate information

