## **Intervention including time plan**

A team consisting of one of the mentors from Fitforlife, a health pedagogic, and one or two from the research group will come to each included open care unit.

Day 1; Upstart meeting led by a research group member.

Day 1-4; Education of the new mentors led by the health pedagogic assisted by mentor(s) from Fitforlife pilot study.

Day 1-5; Baseline examinations (see above for data collection tools) of all the potential participants by the local contact person(s).

Day 5-14; Start of the training. Initially supported by the health pedagogic and the mentor(s) from Fitforlife pilot study.

Day 14-70: Training sessions led by the local mentors. Supported by phone and online by the health pedagogics and the mentors from Fitforlife. During this time 1-3 visit(s) from the health pedagogic to each mentor during a training session.

Day 70-75: Follow up assessments by the local contact person.

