### **Statistical analysis plan**

Baseline descriptions will be presented and used in the different analyses to see if gender, duration of psychosis, neuroleptics affects the different outcomes.

The main outcome social function will be analyzed using  $\chi^2$  tests and analysis of variance for categorical outcomes using data from baseline to 6 months. Pre- to post-intervention (within-group) analyses will be performed using paired-sample *t*tests, with effect sizes (Hedges' *g*) calculated for statistically significant values. The participants will be divided according to attended number of training sessions. This will be done in quartiles and used to look at between group differences (analysis of covariance- ANCOVA). A sub analysis will be done including those with accelerometer data from the entire study period. Baseline score will be included as covariates in each model.

Parametric test assumptions will be checked before running all analyses. Normality will be assessed using the Shapiro–Wilks test and normal probability plot, and homogeneity of variance using Levene's test. For analyses involving unequal sample sizes, Welch's test might be considered. Similar procedures will be used when analyzing blood samples, inflammatory and metabolic markers as well as cognitive test data. Normative data from the cog state data base will be used for comparison. Multilevel analysis will be used taking into account the included open care units.

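### The paired pre-post tests on Trail Making and Cogstate cannot separate training from change that also occurs without it, and the SAP does not make the attendance comparison the basis for conclusions

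*SAP*

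**What the plan says.** The protocol's variables list names Cogstate and Trail Making A and B as the cognitive tests. Its time plan puts baseline examinations at Day 1-5 and the repeat at the end of training: "Day 70-75: Follow up assessments by the local contact person". The design is non-randomised and open, and no untreated group is described.

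For the main outcome, social function, the SAP plans paired t-tests from before to after the intervention, with Hedges' g for significant results. It also plans an ANCOVA between quartiles of sessions attended, baseline score as a covariate in each model, and a multilevel analysis for the care units. It then extends this to cognition: "Similar procedures will be used when analyzing blood samples, inflammatory and metabolic markers as well as cognitive test data". For Cogstate it adds: "Normative data from the cog state data base will be used for comparison".

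The protocol's pilot section gives the only change data. Trail Making A "improved 8.5 seconds (SD 20.4) in those that attended >1 session and 5.4 (SD 6.5) in those that did not attend". Trail Making B "improved 10.4 seconds (SD 42.8) in attenders versus 4.6 (SD 31.7) in non-attenders". On attendance: "Of the 99 persons 39 did not attend any sessions".

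Neither document mentions retest gain, alternate forms or a correction for change that occurs without training.

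**The concern.** A gain in people who attended no session cannot come from the sessions. It may be learning from the first test, usual care, recovery or regression to the mean. The documents do not say which, and the weakness is the same in each case: a single-group paired test counts all of it as improvement. The SAP would then attach an effect size to any significant result.

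The protocol's background lists cognitive dysfunction among the problems that lack effective treatment, so a significant pre-post gain would attract attention. Read alone, it could be taken as a cognitive benefit of exercise when there is none.

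**Working it through.** The plan gives no power, alpha or effect size for cognition, so there is no stated figure to reproduce. The check asks what the planned paired test would show if training did nothing.

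**Inputs (protocol, pilot section and Methodology).** Attenders' gain: A 8.5 s (SD 20.4), B 10.4 s (SD 42.8). Non-attenders' gain: A 5.4 s (SD 6.5), B 4.6 s (SD 31.7). Of 99 included, 39 had no session, leaving 60. Recruitment aim: 300.

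**Assumptions.** Two-sided alpha 0.05; 300 is the trial total (the wording could also mean per unit); attendance as in the pilot; everyone retested unless stated; cognition is retested at Day 70-75.

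**1. Interval.** From 70 - 5 = 65 to 75 - 1 = 74 days, that is 9.3 to 10.6 weeks.

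**2. Share of the gain seen without training.** A: 5.4/8.5 = 64%. B: 4.6/10.4 = 44%. The remainder is 3.1 s and 5.8 s.

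**3. Precision of the remainder.** The numbers retested are not given; 60 and 39 are the maximum.
- A: SE = sqrt(20.4²/60 + 6.5²/39) = 2.83; 3.1 ± 1.96 × 2.83 gives -2.5 to 8.7 s; Welch p = 0.28.
- B: SE = sqrt(42.8²/60 + 31.7²/39) = 7.50; 5.8 ± 1.96 × 7.50 gives -8.9 to 20.5 s; Welch p = 0.44.

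**4. The paired test on the same pilot attenders (n = 60).**
- A: t = 8.5/(20.4/√60) = 3.23, p = 0.002.
- B: t = 10.4/(42.8/√60) = 1.88, p = 0.065.

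So on A the within-group test is significant and the between-group comparison is not. With only 30 and 15 retested the pattern on A is the same (paired p = 0.030, Welch p = 0.45).

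**5. The new trial with no training effect.** Attenders: 60/99 = 61%, and 61% of 300 = 183. Give them only the non-attenders' gain, with the attenders' SD.
- A: t = 5.4/(20.4/√183) = 3.58, p < 0.001.
- B: t = 4.6/(42.8/√183) = 1.45, p = 0.15.

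These are expected values of t. By noncentral t, the chance of a significant result is about 95% on A and 30% on B. The expected t on A stays above 1.96 down to (1.96 × 20.4/5.4)² ≈ 55 retested attenders. On B it would need (1.96 × 42.8/4.6)² ≈ 333.

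**6. Where the quartile cuts fall.** If 39% have zero sessions, that is 117 of 300. The lowest quartile holds 75, so 117 - 75 = 42 people with zero sessions belong in the second. The first cut lies among tied zeros. If quartiles are formed among attenders only, no untrained reference remains.

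**7. Power to detect the pilot's net difference** (change scores, no gain from covariates, no loss from clustering).
- Top against bottom quartile, 75 each: about 15% to 24% on A and 13% to 15% on B. The range comes from using the attenders' SD or the root mean square of the two SDs.
- All 183 attenders against 117 with zero sessions: A, SE = sqrt(20.4²/183 + 6.5²/117) = 1.62, 3.1/1.62 = 1.91, power about 48%. B, SE = sqrt(42.8²/183 + 31.7²/117) = 4.31, 5.8/4.31 = 1.34, power about 27%.

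**The case against.** The strongest reply is that the SAP already holds the remedy. The procedures carried over to cognition include the ANCOVA as well as the paired test. A gain common to all attendance groups cancels there, and with pilot-like attendance the lowest quartile would consist wholly of people with zero sessions. This largely stands: a reader might infer that the plan has no between-group look at cognition, and that would be wrong. What remains is that the SAP does not rank the two analyses, and that quartiles would split the zero-session participants arbitrarily.

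A reader might also infer that a retest gain will be reported as an exercise effect. The documents do not support that. The SAP has no rule that the paired test decides such a claim, and the objectives are held in separate information. It could happen if the within-group result is read alone.

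Three limits on the evidence also stand. The non-attenders' change is not shown to be retest learning. The ratios come from Trail Making only, the numbers retested are unknown, and the attender figure is for more than one session, so people with exactly one may be in neither group. The no-effect demonstration reaches significance on A but not, in expectation, on B.

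The Cogstate norms could help if they are test-retest norms. Against a cross-sectional norm, a gain from repetition still looks like improvement. The SAP does not say which they are, and they do not cover Trail Making.

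**Conclusion.** The concern holds for the within-group cognitive analysis. In the pilot, change without training was 64% of the attenders' gain on Trail Making A and 44% on B, both imprecise. A gain of that size alone would very probably make the paired test significant on A (expected t about 3.6). On B the expected t is about 1.5, not significant, although the chance of a significant result is still well above 5%. For Cogstate the reasoning applies, but the documents give no figures to size it.

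This rests on pilot-like attendance, 300 in total, the attenders' SD and complete retesting. The result for A is not sensitive to moderate loss.

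Severity is moderate. Social function is the main outcome, the protocol declares the lack of randomisation as a limitation, and a partial remedy is already planned.

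**What to change.** Change the SAP wording as follows.

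1. Label the paired cognitive results, and any movement toward the Cogstate norm, as descriptive.
2. Base any statement about exercise and cognition on the baseline-adjusted, multilevel contrast by attendance. Keep zero-session participants as one separate reference group and divide only the attenders further.
3. Show the zero-session group's change beside every pre-post cognitive result, described as change without training rather than as retest gain. Give the number retested in each group.
4. State whether the Cogstate norms are cross-sectional or test-retest.

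This uses assessments already planned, provided zero-session participants are retested; the time plan does not say who is. The cost is in the message. The cognitive gain will look smaller, and the contrast is less precise than the paired test, with about 48% (A) and 27% (B) power for the pilot's net differences. Attendance is self-selected, so the contrast removes shared change but does not prove causation, and the SAP should say so. A practice run before baseline or an alternate form at follow-up is optional; the documents do not show that either would remove the shared change.

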## **Methodology**

Study design: Non randomized open trial.

*Study population:* Patients affected by psychosis at open care psychiatric units who are responsible for taking care of psychosis in Sweden.

*Sample size:* Our aim is to recruit 300 patients including mentors at each unit.

*Variables list including data collection tools:*

1. From the medical records: age, gender, diagnosis, time of first contact with psychiatry, medication
  - App questions on overall function using WHODAS 2.0
  - App question on social network: qualitative and quantitative
  - App questions: smoking, alcohol consumption and illicit drug use
  - Cognitive tests: Cogstate (performed at a computer) and Trail making A and B
  - Submaximal fitness test: Åstrand
  - Physical activity pattern, including sedentary time, low-intensity physical activity and exercise, assessed by a simple accelerometer on a subsample.
  - Body measurements: length, weight, hip-waist measure, blood pressure.
  - Blood samples: Blood lipids, HBA1C, TNFalfa, CRP, Il-6

*Plan of analyses:* See separate information

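### The SAP repeats its significance tests over at least nine outcomes without an alpha, a decisive main analysis, multiplicity control or an exploratory label, and gives effect sizes only for significant results

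*SAP*

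**What the plan says.** All the analysis text is in the SAP, under Statistical analysis plan.

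- **Main outcome.** One domain is named: "The main outcome social function will be analyzed using" chi-square tests and analysis of variance. Paired t tests and an ANCOVA across quartiles of attendance follow. The SAP does not name the instrument for social function. The Protocol's variables list (Methodology) offers two candidates: "App questions on overall function using WHODAS 2.0" and "App question on social network: qualitative and quantitative".
- **Extension to other outcomes.** "Similar procedures will be used when analyzing blood samples, inflammatory and metabolic markers as well as cognitive test data". The Protocol lists them as "Blood samples: Blood lipids, HBA1C, TNFalfa, CRP, Il-6" and "Cognitive tests: Cogstate (performed at a computer) and Trail making A and B". Body measurements are a separate line there.
- **Patient factors.** Baseline descriptions will be used to "see if gender, duration of psychosis, neuroleptics affects the different outcomes".
- **Effect sizes.** For the within-group comparisons, Hedges' g is "calculated for statistically significant values".

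The SAP contains no significance threshold, multiplicity adjustment, testing order or exploratory label. The Protocol refers to separate information for the study objectives, and that information is not among the documents.

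**The concern.** When the same tests are run over many outcomes at an unadjusted level, some are likely to reach significance by chance alone. The reader then cannot tell these from real findings, because the plan does not say how a secondary result is to be weighed.

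Two features add to this. First, significance decides which pre-post changes receive an effect size. An estimate reported only because its test was significant is too large on average, so the rule affects the published size of effects as well as the p-values. Second, the main outcome gives less protection than it should, because several analyses of it are planned and any of them could be presented as the main result.

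At stake is the interpretation of the secondary results and, to a lesser degree, of the main one. Feasibility and conduct are not affected.

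**Working it through.** The documents give no alpha, number of tests or error rate, so there is no figure of the plan's own to reproduce. The check counts the tests and works out what follows.

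**Outcomes** (Protocol, Methodology; scope from the SAP)
- Social function: 1
- Blood: lipids counted once, HbA1c, TNF-alpha, CRP, IL-6 = 5
- Cognition: Cogstate counted once, Trail Making A, Trail Making B = 3
- Clearly covered by the SAP: 1 + 5 + 3 = 9
- Weight, hip-waist and blood pressure = 3, only if body measurements are read as metabolic markers: 9 + 3 = 12

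**Tests per outcome** (SAP)
- Paired t test and attendance-quartile ANCOVA: 2
- Gender, duration of psychosis and neuroleptics, if each is tested separately: 3 more, so 5

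**Assumptions**
- Two-sided alpha of 0.05
- Global null: every tested difference is truly zero
- Pairwise correlation ρ between test statistics of 0 or 0.5

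**Formulas**
- Expected false positives = m × 0.05, where m is the number of tests. This holds whatever the correlation.
- Chance of at least one, independent tests = 1 − 0.95^m.
- Chance of at least one, ρ = 0.5 = 1 − E[{Φ((1.96 − √ρ·U)/√(1−ρ)) − Φ((−1.96 − √ρ·U)/√(1−ρ))}^m], with U standard normal, by numerical integration.

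| Reading | m | Expected false positives | At least one, ρ = 0.5 | At least one, independent |
|---|---|---|---|---|
| 9 outcomes, factors as covariates | 9 × 2 = 18 | 0.9 | 40% | 60% |
| 12 outcomes, factors as covariates | 12 × 2 = 24 | 1.2 | 46% | 71% |
| 9 outcomes, factors tested | 9 × 5 = 45 | 2.25 | 60% | 90% |
| 12 outcomes, factors tested | 12 × 5 = 60 | 3.0 | 66% | 95% |

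**Sensitivity to alpha.** At 0.01, 18 to 60 tests give 0.18 to 0.6 expected false positives; at 0.10 they give 1.8 to 6.0.

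**What the count leaves out.** It omits the chi-square and ANOVA analyses, the accelerometer sub-analysis and the comparison with Cogstate norms (all in the SAP). It also omits the social network question as a separate outcome, fitness and substance use. Separate lipids or Cogstate subtests would raise it further.

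**The case against.** The strongest reply is that the plan does name one main outcome, so the main conclusion does not compete on equal terms with a blood marker. Many analysts would also accept unadjusted secondary results if they were labelled exploratory. Part of this stands: the main outcome gives some protection, and false-discovery control in two families is one reasonable choice among several. The protection is incomplete, however, because neither the instrument nor the decisive analysis is named, and the exploratory label is absent. A hierarchy may exist in the separate study objectives, which cannot be seen here.

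A reader might infer that the plan commits to at least 60 tests, about three of which will be significant with no effect at all. The documents do not support that, for these reasons:

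- Thirty-six of the 60 (12 × 3) come from reading the sentence on the three factors as separate tests. It fits covariates in a model equally well.
- Twelve outcomes is not a minimum. The SAP clearly covers nine, and it does not name body measurements.
- The 5% level is an assumption.
- Three is an average, not a prediction. With 60 independent tests the chance of no false positive is still 0.95^60 = 4.6%, and on the other readings in the table it is larger.

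The sentence on similar procedures also follows directly after the assumption checks and could refer to those alone. Carry-over of the tests is the likelier reading but is not certain.

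Finally, chance is not the only threat. The trial is open and non-randomised, and the paired tests have no control group. In the pilot, non-attenders improved by 5.4 seconds (SD 6.5) on Trail Making A (Protocol, Preliminary results Fitforlife pilot study). A change of that kind can be significant without being a false positive in the sense used here, and no multiplicity adjustment would remove it. This objection stands in full as a limit on what the fix can do.

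**Conclusion.** The concern holds at moderate size. At an assumed two-sided 5% under a global null, the plan implies about one expected false positive if the three factors are only covariates, and about two to three if each is tested. The chance of at least one is 40–71% in the first case and 60–95% in the second. A significant secondary result arising by chance is therefore quite possible to very likely, depending on the reading, but not certain. Even the smallest count leaves the chance far above 5%.

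These figures rest on nine to 12 outcomes, on the paired test and the ANCOVA being carried over to all of them, and on correlation between 0.5 and 0. The absence of an alpha, a decisive analysis, error control and an exploratory label depends on none of these assumptions, and neither does the rule that ties effect sizes to significance. This is an inexpensive improvement to make before the data are analysed. It is not a defect that invalidates the trial.

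**What to change.** Amend the SAP as follows.

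1. Name the instrument, time point and one analysis of social function as the single confirmatory test, two-sided at 5%. The time point needs settling: the SAP uses data to 6 months, whereas the Protocol's time plan has follow-up assessments on days 70–75 and then medical records to 12 months.
2. Label the other outcomes secondary or exploratory, and report Benjamini-Hochberg adjusted p-values at 5% within two families: cognitive, and metabolic and inflammatory. List the members of each family, stating whether body measurements belong and how lipids and Cogstate are counted.
3. Report the results for gender, duration of psychosis and neuroleptics as estimates with intervals, without significance statements.
4. Report effect sizes with intervals for all outcomes, whether or not significant.

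The cost is SAP wording, with no new data and no change to conduct. The downside is fewer nominally significant secondary results. With two tests per outcome, the cognitive family has 3 × 2 = 6 tests and the other 5 × 2 = 10, or 8 × 2 = 16 with body measurements. A single low p-value in an otherwise null family would then need to be at or below 0.05/6 = 0.0083, 0.05/10 = 0.005 or 0.05/16 = 0.0031. The adjustment deals with chance only; pre-post changes still need to be reported as uncontrolled.
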